### 3.5.2. Derived Variables

Variables derived from abstracted and extracted data will include the following:

- Age at index date (Table 1).
- BMI at index date ( $\pm 30$  days) (Table 1).
- Geographic census region of patient's residence (Table 1).
- Weighted index of comorbid disease condition. Weighting of comorbid conditions will follow the weighting as specified in the Charlson Comorbidity Index (Table 2).
- Start and end dates and start and end dose of infused anti-cancer treatments from the index date through the end of the third R/R-based line of therapy or the end of the record, whichever occurs first.
- Dose changes of all oral (if applicable), infused, or injected anti-cancer therapies from the index date through the end of the first R/R-based line of therapy or the end of the record, whichever occurs first (Table 4).
- Start and end schedule of infused anti-cancer treatments from the index date through the end of the third R/R-based line of therapy or the end of the record, whichever occurs first (Table 3-Table 5).
- Treatment regimens, derived from oral and infused agents delivered, including start and stop dates, and indication of subsequent treatment after 1L (Table 3-Table 5).
- Duration of anti-cancer treatments regimens from the index date through the end of the third R/R-based line of therapy or the end of the record, whichever occurs first. Duration will be calculated as the end date of a regimen minus the start date of the corresponding regimen and will be computed during the analytics phase of the project (Table 5).
- Time under observation for analysis of rwEFS/rwRFS, by line, based on start date of treatment within line and dates of R/R event or disease progression, or censoring (Table 5-Table 7).
- Time under observation for analysis of rwOS from start of the first qualifying Mylotarg-containing R/R-based line of therapy, based on start of treatment in the first qualifying line setting, and based on date of death or censoring (Table 8).

- Time to best response for each regimen in the first qualifying Mylotarg-containing R/R-based line of therapy from the index date through the end of the third R/R-based line of therapy or the end of the record, whichever occurs first (Table 9-Table 11, Table 14-Table 15).
- Duration of response for each regimen in the first qualifying Mylotarg-containing R/R-based line of therapy from the index date through the end of the third R/R-based line of therapy or the end of the record, whichever occurs first (Table 11).

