### 4.2. Regimens and Lines

For purposes of this study, a **regimen** will be defined as 1 or more anti-cancer agents given in combination, over a period of time, in which the following conditions hold:

1. All agents start within 30 days of the start of the first agent in the combination, unless the start of an agent later than 30 days after the start of the first agent is specifically indicated as planned at the time of the start of the first agent.
2. No agent is discontinued and replaced by another agent within 30 days of the start of the first agent in the combination.
  - a. All agents in the regimen must be discontinued for the regimen to be considered as discontinued. If only a single agent within a regimen is discontinued after 30 days, the regimen is assumed to be ongoing so long as the other agents are not yet discontinued.
3. No agent is held and then resumed after an interval of more than 63 days. A standard chemotherapy cycle is assumed to be 21 days; 63 days allows for a delay of 3 cycles of chemotherapy without a change in regimen.

Please note: These conditions do not dictate how detailed information about oncology medications is captured, or how medication start and end dates are recorded, regardless of the days' supply of any given prescription. Rather, the conditions are only used to define lines of therapy, and information about medications and days' supply is recorded as documented in the medical record.

Accordingly, unless the record indicates a planned delay in the start of an agent, the addition of a new agent to an existing therapy more than 30 days after start of the regimen constitutes a change of regimen. Holding of an agent for a brief period is not interpreted as a change of regimen. However, discontinuation and resumption of an agent after an interval of more than

63 days is interpreted as signaling a new regimen. Discontinuation of all agents in a regimen signals the end of the regimen. Occurrence of an R/R event or a disease progression does signal the end of a regimen. Continuation after R/R event or progression of a treatment being given before the R/R event or progression will be interpreted as a new regimen—albeit identical to the previous one. This scenario, treatment through progression, occurs in some settings, and is identifiable in study data with the coding rules described here.

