#### 4.3.2. Time to Event Analysis

Single time to event analyses will be conducted as specified under the study objectives. CCI [REDACTED]

Real-world time to event outcomes in this study will include:

- rwEFS/rwRFS for the first 3 R/R-based lines of therapy. rwEFS will be defined as the time from the treatment initiation date (for the first agent in the first regimen in the first line of Mylotarg-containing therapy) to the date of treatment failure (TF), relapse from Complete Response (CR) or better, or death from any cause, whichever comes first. TF is defined as failure to achieve CR or better following up to 3 cycles of Mylotarg. rwRFS will be defined as the time from the treatment initiation date (for the first agent in the first regimen in the first line of therapy) to the date of a relapse event, or death from any cause, whichever comes first.
- rwOS, from the first line of therapy through the end of record or death, whichever occurs first, and
- Duration of therapy across lines of therapy from the first line of therapy through the third R/R-based line of therapy.

The time origin for analysis of rwEFS/rwRFS is the start of therapy within each specific line of therapy, and the terminal event is the earlier of an R/R event or death. The time origin for analysis of rwOS is the start of therapy within the first line of therapy, and the terminal event is death. Patients who are not indicated to be deceased at last known contact (patients who are alive, or lost to follow-up) will be censored. The time origin for analysis of duration of therapy is start of Mylotarg, and the terminal event is discontinuation of that therapy.

#### 4.3.3. Methods under Objective 1

*Objective 1: To describe the demographic and clinical characteristics as outlined in the variable list below for patients diagnosed with AML who received Mylotarg in a real-world setting.*

Descriptive analysis as detailed in [Section 4.3.1](#) will be conducted for work under this objective. Demographic characteristics that will be reported will include sex, patient age, race/ethnicity, height, weight, BMI, insurance status, and region of residence closest to the index date. Clinical characteristics that will be reported will include comorbidities and comorbidity index score, ECOG score, and disease characteristics, such as stage at index date, cytogenetic testing at index date, and whether the AML diagnosis was de novo versus secondary.

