**Table 5. Mylotarg Treatment Duration, by Line of Therapy**

Mylotarg Treatment Duration		N=xxx
First Line Therapy		
n		xx
Mean		x.x
SD		x.x
1 st Quartile		x.x
Median		x.x
3 rd Quartile		x.x
IQR		x.x
Min, Max		x.x,x.x
N=xxx		
Second Line Therapy		
n		xx
Mean		x.x
SD		x.x
1 st Quartile		x.x
Median		x.x
3 rd Quartile		x.x
IQR		x.x
Min, Max		x.x,x.x
N=xxx		
Third Line Therapy		
n		xx
Mean		x.x
SD		x.x
1 st Quartile		x.x
Median		x.x
3 rd Quartile		x.x
IQR		x.x
Min, Max		x.x,x.x

\* The time origin was the initiation of Mylotarg. The end point was the last date of gemtuzumab therapy, regardless of line of therapy (duration could continue into subsequent lines of therapy), study end date, or death, whichever came first.

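### The SAP gives Table 5 (Mylotarg duration by line) incompatible rules: regimen length in 3.5.2, Mylotarg's own dates in 4.3.2 and the table footnote

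*SAP*

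**What the plan says.** Objective 2d (SAP section 2) asks how long Mylotarg was given in each of the first three R/R-based lines. The output is Table 5, titled "Mylotarg Treatment Duration, by Line of Therapy". The text bearing on how it is filled is in four places.

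- **SAP 3.5.2.** The bullet on regimen duration, tagged to Table 5, reads: "Duration will be calculated as the end date of a regimen minus the start date of the corresponding regimen". Protocol 9.3.4 has the same variable, with the end set at the end date of the regimen's last agent, and names no table. SAP 3.5.2 lists no duration specific to Mylotarg.
- **SAP 4.2.** On when a regimen ends: "All agents in the regimen must be discontinued for the regimen to be considered as discontinued". If a single agent stops after 30 days, "the regimen is assumed to be ongoing so long as the other agents are not yet discontinued". A second route closes a regimen: "Occurrence of an R/R event or a disease progression does signal the end of a regimen". On when it begins: "All agents start within 30 days of the start of the first agent in the combination", with a later start allowed if it was planned.
- **SAP 4.3.2** (and Protocol 9.7.2): "The time origin for analysis of duration of therapy is start of Mylotarg, and the terminal event is discontinuation of that therapy". SAP 4.2 defines discontinuation agent by agent.
- **Table 5 footnote:** "The time origin was the initiation of Mylotarg. The end point was the last date of gemtuzumab therapy, regardless of line of therapy". It adds that duration can carry on into later lines, and that study end or death closes the interval if earlier.

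**The concern.** A regimen's length and Mylotarg's own duration are different quantities whenever Mylotarg is given with other agents and does not both start first and finish last. SAP 3.5.2 is the SAP's list of derived variables, and Protocol 9.3.4 leaves the formal definition of analysis variables to the SAP. A programmer working from that list would put regimen lengths into a table labelled as Mylotarg duration. One working from the footnote would put something else there. Objective 2d would then depend on which section was read, and a reader of the report could not tell which rule had been used. With 20 to 30 patients spread over up to three lines, a few long regimen lengths can move the mean, upper quartile and maximum of a Table 5 block.

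**Working it through.** The documents give no duration figure to reproduce, so the check sets the rules side by side and applies them to assumed dates.

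**The rules**

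| Source | Start | End | Confined to the line? |
|---|---|---|---|
| SAP 3.5.2 with 4.2 | First agent of the regimen | Last agent stops, or R/R event or progression | Yes, but covers all agents |
| SAP 4.3.2 | Mylotarg start | Mylotarg discontinued | Not stated |
| Table 5 footnote | Mylotarg start | Last Mylotarg date, study end or death | No |
| Objective 2d, Table 5 title | Mylotarg | Mylotarg | Yes |

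No rule in the SAP meets both requirements of Objective 2d, which are Mylotarg only and within the line.

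**Dates applied.** All days are assumptions. Duration is end minus start, as in 3.5.2. Cases A to E lie within one line, with no R/R event or progression.

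| Case | Regimen rule | First to last Mylotarg date | Difference (days) |
|---|---|---|---|
| A. Regimen days 1–120, Mylotarg days 1–7 | 120 − 1 = 119 | 7 − 1 = 6 | +113 |
| B. As A, with a second Mylotarg course on days 60–66 | 119 | 66 − 1 = 65 | +54 |
| C. Mylotarg days 1–7, last companion agent ends day 7, 30 or 90 | 6, 29 or 89 | 6 | 0, +23 or +83 |
| D. First agent day 1, Mylotarg days 31–37, all agents end day 37 | 37 − 1 = 36 | 37 − 31 = 6 | +30 |
| E. Mylotarg alone, days 1–7 and 71–77 | 6 and 6 (two regimens) | 77 − 1 = 76 | 12 − 76 = −64 |

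Notes on the cases:

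- **A.** Mylotarg stops on day 7, before the 30-day point in the single-agent sentence of 4.2. The case rests on the sentence before it, which requires all agents to stop and has no such limit.
- **B.** The Mylotarg gap is 60 − 7 = 53 days, under the 63-day limit, so it remains one regimen.
- **C.** Mylotarg exposure is identical throughout, and only the companion drug changes the answer.
- **D.** The 30-day joining window adds up to 30 days at the front, and more if a later start was planned.
- **E.** The gap is 71 − 7 = 64 days, over 63, so 4.2 starts a new regimen. With no R/R event or progression the line is unchanged. The regimen rule now gives shorter values, and nothing says how two regimens in one line enter a single row of Table 5.

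**Across lines.** Suppose Mylotarg is given on days 1–7 in line 1, an R/R event closes the regimen on day 30, and Mylotarg is given again on days 60–66 in line 2. For line 1, the regimen rule gives 30 − 1 = 29 days and the footnote gives 66 − 1 = 65. Mylotarg's own duration within line 1 is 6 days, and within line 2 it is 66 − 60 = 6.

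**The case against.** The strongest reply is that the SAP already has the right rule where it matters. The footnote sits directly under Table 5 and is specific to Mylotarg. SAP 4.3.2 and Protocol 9.7.2 agree with it, and discontinuation is defined per agent. The table tags in 3.5.2 are loose: the bullet on observation time for rwEFS and rwRFS is tagged to Tables 5 to 7, though those endpoints belong in Tables 6 and 7. Regimen duration also has a legitimate use of its own, since SAP 4.3.4 plans duration of treatment across lines starting from the first agent or regimen. Finally, this is a descriptive output. SAP 4.1 does not list treatment patterns among the primary endpoints, and no comparisons are planned.

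Most of that stands, and it rules out two stronger readings.

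- A reader might infer that the SAP has settled on counting companion time as Mylotarg exposure. It has not, because the footnote and 4.3.2 both exclude that time. An R/R event or progression also limits how far a regimen can run.
- A reader might infer that only patients on combinations are affected, so that they would look longer-exposed than patients on Mylotarg alone. Case E shows that the rules can also part for Mylotarg alone, in the other direction. Table 5 has no split by combination use in any case.

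The reply does not remove the conflict. The tag on the regimen-duration bullet is explicit, 3.5.2 offers no competing Mylotarg variable, and no other table shell reports regimen duration. The footnote cannot simply be preferred either, because it crosses lines while the objective and the table title do not.

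**Conclusion.** The point holds as an internal contradiction: incompatible rules are stated for one output, and none of them gives Mylotarg's own duration within a line. If 3.5.2 is followed, the excess over Mylotarg's own duration in a combination regimen runs from zero, when Mylotarg starts first and ends last, to the whole companion lead-in and tail. That is 113 days in case A. Where a gap over 63 days splits the regimen, the rule can instead fall short. These sizes rest on assumed dates, and the documents give no basis for saying how often such patterns will occur among the 20 to 30 patients. The matter affects a secondary descriptive objective and no primary endpoint. It should still be corrected, because the candidate rules can differ several-fold for the same patient and the repair is cheap.

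**What to change.** 1. In SAP 3.5.2, remove the Table 5 reference from the regimen-duration bullet. Report regimen duration in its own labelled rows or table under Objective 2, where SAP 4.3.4 already calls for it.
2. Add to 3.5.2 a Mylotarg-specific duration tagged to Table 5: last Mylotarg date within the line minus first Mylotarg date within the line. This is consistent with 4.3.2 and answers Objective 2d.
3. Amend the Table 5 footnote so that the interval stops at the end of the line, and add the same boundary to 4.3.2. If the sponsor also wants total Mylotarg duration across lines, give it a separate row.
4. State how Mylotarg gaps of more than 63 days within a line are counted. In case E the full span is 76 days and the sum of the two courses is 6 + 6 = 12, so the choice has to be written down.

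The cost is SAP wording, one derived variable and a few table rows. SAP 3.5.1.1 and 3.5.1.2 already provide for treatment dates by agent, so no new abstraction is needed.

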## 4. STATISTICAL METHODS

### 4.1. Endpoints

The primary study endpoints are effectiveness outcomes of rwEFS/rwRFS, rwOS, and response. Patient demographics and clinical characteristics, as well as treatment patterns will also be evaluated.

### 4.2. Regimens and Lines

For purposes of this study, a **regimen** will be defined as 1 or more anti-cancer agents given in combination, over a period of time, in which the following conditions hold:

1. All agents start within 30 days of the start of the first agent in the combination, unless the start of an agent later than 30 days after the start of the first agent is specifically indicated as planned at the time of the start of the first agent.
2. No agent is discontinued and replaced by another agent within 30 days of the start of the first agent in the combination.
  - a. All agents in the regimen must be discontinued for the regimen to be considered as discontinued. If only a single agent within a regimen is discontinued after 30 days, the regimen is assumed to be ongoing so long as the other agents are not yet discontinued.
3. No agent is held and then resumed after an interval of more than 63 days. A standard chemotherapy cycle is assumed to be 21 days; 63 days allows for a delay of 3 cycles of chemotherapy without a change in regimen.

Please note: These conditions do not dictate how detailed information about oncology medications is captured, or how medication start and end dates are recorded, regardless of the days' supply of any given prescription. Rather, the conditions are only used to define lines of therapy, and information about medications and days' supply is recorded as documented in the medical record.

Accordingly, unless the record indicates a planned delay in the start of an agent, the addition of a new agent to an existing therapy more than 30 days after start of the regimen constitutes a change of regimen. Holding of an agent for a brief period is not interpreted as a change of regimen. However, discontinuation and resumption of an agent after an interval of more than

63 days is interpreted as signaling a new regimen. Discontinuation of all agents in a regimen signals the end of the regimen. Occurrence of an R/R event or a disease progression does signal the end of a regimen. Continuation after R/R event or progression of a treatment being given before the R/R event or progression will be interpreted as a new regimen—albeit identical to the previous one. This scenario, treatment through progression, occurs in some settings, and is identifiable in study data with the coding rules described here.

A discontinuation will be defined as stopping of a particular agent for any reason, as indicated by provider documentation of “discontinuation” or “change in therapy” in the medical record, or, in the absence of provider documentation of discontinuation or change in treatment, a change in treatment with a particular agent, with no further treatment with that agent documented in structured data, or, evidence that the patient is admitted to hospice care (as the assumption is made that all systemic therapy is discontinued at that time).

For purposes of this study, first line therapy will be defined as beginning with the first regimen the patient receives after diagnosis of the disease of interest. Subsequent lines in this study will be defined as *R/R-based lines*. *R/R-based lines* are defined by the occurrence of an R/R event or a disease progression - either may be cited, in which an R/R event or disease progression must occur for a new regimen to be interpreted as a new line of therapy. In this study, **refractory** AML is defined as disease that is nonresponsive or failing to achieve at least minimal response while on therapy. **Relapsed** status is defined as the recurrence or worsening of disease following achievement of at least a minimal response. Additionally, the documentation of advancement of disease in patients after initial AML diagnosis but before initial AML treatment will be interpreted as a disease progression. R/R events and disease progression will be defined based on provider documentation, which primarily includes progress notes.

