*R/R-based lines* are defined by the occurrence of a R/R event or a disease progression - either may be cited, in which a R/R event or disease progression must occur for a new regimen to be interpreted as a new line of therapy. R/R-based lines may be preferred where the research questions focus on effectiveness outcomes such as rwEFS/rwRFS, and where sample homogeneity as to previous disease progression is preferred for assessment of outcomes in second or later lines. In this study, refractory AML is defined as disease that is nonresponsive or failing to achieve at least minimal response as noted by provider documentation (described in [Section 9.7.6](#)) while on therapy. Relapsed status is defined as the recurrence or worsening of disease following achievement of at least a minimal response. Additionally, the documentation of advancement of disease in patients after initial AML diagnosis but before initial AML treatment will be interpreted as a disease progression. R/R events and disease progression will be defined based on provider documentation, which primarily includes progress notes.

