rwEFS will be defined as the time from the treatment initiation date (for the first line of Mylotarg-containing therapy) to the date of treatment failure (TF), relapse from CR or better, or death from any cause, whichever comes first. TF is defined as failure to achieve CR or better following up to 3 cycles of Mylotarg. Accordingly, the time origin for rwEFS will be the start of Mylotarg in the first line of therapy in which it is used. The terminal event for analysis of rwEFS is the earlier of treatment failure, relapse from CR or better (as evidenced by provider documentation), or death. Patients who have not died or experienced an event by the date of last contact within the medical record will be censored for analysis of rwEFS.

rwRFS will be defined as the time from the treatment initiation date (during the first line of Mylotarg-containing therapy) to the date of a relapse event, or death from any cause, whichever comes first. The time origin for rwRFS will be the start of Mylotarg in the first line of therapy in which it is used. The terminal event for analysis of rwRFS will be the earlier of a relapse event (as evidenced by provider documentation), or death. Patients who have not died or experienced a relapse event by the date of last contact within the medical record will be censored for analysis of rwRFS.

The time origin of rwOS analysis is the start of the first Mylotarg use. The terminal event for analysis of rwOS is date of death. Note that Social Security Disability Insurance (SSDI) records have an expected lag of up to 4 months. Accordingly, patients who are not indicated to be deceased in clinical records or SSDI records will be censored for rwOS analysis as of the later of 1) the latest date known alive within the clinical record, 2) 4 months prior to the date of most recent SSDI update.

Separate Kaplan-Meier analyses will be conducted for each rwEFS, rwRFS and rwOS endpoint.

#### 4.3.6. Methods under Objective 4

*Objective 4: To evaluate response among AML patients who received Mylotarg in a real-world setting.*

- a. First and best response for each regimen in the first qualifying Mylotarg-containing R/R-based line of therapy.
- b. Time to best response for each regimen in the first qualifying Mylotarg-containing R/R-based line of therapy.
- c. Duration of best response for each regimen in the first qualifying Mylotarg-containing R/R-based line of therapy.

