Response will be assessed for the first and best overall response to treatment for each regimen in the first qualifying Mylotarg-containing R/R-based line of therapy during the study period. Response classifications will be made based on the treating physician's documentation of response itself, typically informed by radiological scan reports noted in the patient record. Classification is made to the following categories: complete response (CR), partial response (PR), stable disease (SD), progressive disease (PD), and not evaluable (NE), each based on the treating physician's statements. In cases where complete response with partial hematologic recovery (CRh), complete response with incomplete hematologic recovery (CRi), and morphologic leukemia-free state (MLFS) are explicitly included in the treating physician's statements, these additional classifications will be documented. The date of the best overall response for each regimen in the first qualifying Mylotarg-containing R/R-based line of therapy will be collected. Responses captured are based on treating physician's assessment in the medical record. Overall response rate will be defined as a percentage of patients whose best response is either CR, CRi, or MLFS, where available. Time to best response and duration of best response will be assessed using the descriptive techniques described above.

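### Relapse has one threshold for lines of therapy, a stricter one in rwEFS and none stated in rwRFS, so whether worsening after a partial response is an rwRFS event depends on the section used

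*SAP*

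**What the plan says.** SAP 4.1 lists rwEFS/rwRFS among the primary endpoints. The passages that bear on relapse are these.

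- **Definition of relapse.** SAP 4.2 says that relapsed "status is defined as the recurrence or worsening of disease following achievement of at least a minimal response". Protocol 9.3.1 says the same. Neither document gives any other general definition.
- **Definition of refractory.** SAP 4.2 uses the same threshold: "disease that is nonresponsive or failing to achieve at least minimal response while on therapy". Protocol 9.3.1 has "failing to achieve at least minimal response as noted by provider documentation (described in" and then refers to its Section 9.7.6.
- **Response categories.** SAP 4.3.6 lists "complete response (CR), partial response (PR), stable disease (SD), progressive disease (PD), and not evaluable (NE), each based on the treating physician's statements", and adds CRh, CRi and MLFS where the physician names them. Tables 9 and 10 add Other Favorable and Other Unfavorable.
- **rwEFS.** SAP 4.3.2 counts "relapse from Complete Response (CR) or better, or death from any cause, whichever comes first", together with treatment failure. SAP 4.3.5 repeats this: "The terminal event for analysis of rwEFS is the earlier of treatment failure, relapse from CR or better (as evidenced by provider documentation), or death".
- **rwRFS.** SAP 4.3.5: "The terminal event for analysis of rwRFS will be the earlier of a relapse event (as evidenced by provider documentation), or death". The clock starts with the drug and not at remission: "The time origin for rwRFS will be the start of Mylotarg in the first line of therapy in which it is used". Table 7 covers all patients.
- **Competing rules.** The closing paragraph of SAP 4.3.2 ends both endpoints at the first of an R/R event and death. Protocol 9.7.5 ends both at the first of death, disease progression and an R/R event.

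**The concern.** In SAP 4.3.5 the rwEFS and rwRFS paragraphs stand next to each other. The first ties relapse to CR or better and the second does not. A programmer who needs a meaning for relapse in rwRFS will find only the one in SAP 4.2, whose threshold is lower and is not a recorded category. Someone who assumes that both endpoints share one meaning of relapse will apply the CR threshold. Both choices can be defended from the text, and they give different event dates for the same patient.

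At stake is what rwRFS measures. With the lower threshold it can include loss of partial control in patients who never reached remission. With the CR threshold in the all-patients set, those patients count as relapse-free until death or censoring. Either estimate could appear in Table 7 under the same title.

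**Working it through.** The plan gives no figure to reproduce, so the check sets the passages side by side for one patient.

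**Step 1. Is minimal response recorded?** The categories are CR, PR, SD, PD, NE, CRh, CRi and MLFS, plus Other Favorable and Other Unfavorable. None is minimal response. Protocol 9.7.6, to which Protocol 9.3.1 points, does not use the term.

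**Step 2. Apply each rule to a patient whose best response is PR and who then worsens.**

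| Rule followed | rwRFS | rwEFS |
|---|---|---|
| SAP 4.3.5, relapse as in 4.2, PR taken to meet minimal response | Event at worsening | Not a relapse; event through treatment failure if CR is not reached following up to 3 cycles |
| SAP 4.3.5, relapse as in rwEFS (from CR or better) | No event at worsening; at risk until death or censoring | As above |
| SAP 4.3.5, worsening abstracted as disease progression | No event at worsening | As above |
| SAP 4.3.2 closing paragraph | Event if abstracted as an R/R event | Same as rwRFS |
| Protocol 9.7.5 | Event whether abstracted as R/R or progression | Same as rwRFS |

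The 3 cycles are the SAP's figure. Protocol 9.7.2 gives 6, a separate discrepancy that also has to be reconciled.

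**Step 3. A patient with SD who then worsens.** If SD meets minimal response, the worsening is a relapse and an rwRFS event under 4.3.5 read with 4.2. If it does not, the disease is refractory, which is not in the 4.3.5 rwRFS event. The text does not settle which.

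**Step 4. Scale.** SAP 3.3 expects 20 to 30 patients.

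- One patient as a share of the sample: 1/30 = 3.3%; 1/20 = 5.0%.
- The documents give no PR rate. Assuming, for illustration only, that 10% to 30% of patients have PR as best response, the number whose status could be in dispute is at most 0.10 × 20 = 2 to 0.30 × 30 = 9. Only those who worsen are affected.

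The resulting shift in the rwRFS median cannot be derived, because it also needs times to worsening and to death that the documents do not give.

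**The case against.** The 4.2 definition stands in the section on regimens and lines, where its job is to build lines of therapy. Both 4.2 and 4.3.5 rest on provider documentation, so the event may simply be whatever the treating physician called a relapse. Worsening in a patient never in remission may be abstracted as disease progression, whose dates are collected alongside R/R dates and which is not in the 4.3.5 rwRFS event. The study is descriptive, with no comparisons.

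Much of this stands, and it rules out three stronger readings that a reader might infer.

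- *That rwRFS must count worsening after PR as relapse.* This is the natural reading of 4.3.5 with 4.2, because 4.2 gives its definition for the study as a whole. No passage compels it.
- *That relapse cannot be recorded because minimal response is not a category.* R/R dates are abstracted directly from notes (SAP 3.5.1.1 and 4.2) and are not derived from response categories. The gap makes the abstraction rule imprecise; it does not block recording.
- *That rwRFS cannot be read beside rwEFS.* A patient who never reaches CR may already be an rwEFS event through treatment failure, so for such patients the lower threshold can bring the two endpoints closer.

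The appeal to provider documentation does not remove the problem. SAP 4.3.5 attaches the same phrase to the rwEFS relapse component, which still carries a CR threshold. The phrase names the source of evidence and does not set the threshold. If 4.2 is held not to apply, rwRFS has no definition of relapse at all.

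**Conclusion.** The point holds as an unresolved definition in a primary endpoint. The documents contain two relapse thresholds, leave rwRFS without one, and add two further rules for ending both endpoints. Worsening after PR is therefore an rwRFS event under some passages and not under others.

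This conclusion rests on the text alone. It does not establish that rwRFS will be biased in a given direction, or by how much: that depends on how many patients reach PR without CR, how their worsening is abstracted, and which passage is programmed. What can be said is that each affected patient carries 3.3% to 5.0% of the sample. The change is worth making before the estimate is reported. The threshold cannot be settled apart from the population in Table 7, because applying the CR threshold to all patients leaves those who never remitted counted as relapse-free.

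**What to change.** 1. In SAP 4.3.2 and 4.3.5, state the rwRFS event as relapse from CR or better, or death, and list the remission categories once for both rwRFS and rwEFS. Say explicitly whether CRh, CRi and MLFS qualify.
2. Remove the closing sentence of SAP 4.3.2 that ends both endpoints at any R/R event, or reconcile it with 4.3.5, and do the same with Protocol 9.7.5.
3. In SAP 4.2, say that the relapsed and refractory wording serves line-of-therapy assignment only. Replace minimal response with a category that 4.3.6 records, for example PR or better.
4. For Table 7 and Figure 2, either report rwRFS in patients who reached the listed remission categories, or keep all patients and add a footnote that those who never remitted count as relapse-free until death or censoring. If the first option is taken, start the clock at the remission date, since the time from Mylotarg start to remission is event-free by selection.

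The cost is mainly wording. R/R dates are already abstracted, and so are responses if they are collected for the first Mylotarg-containing line as 4.3.6 describes. Protocol 9.7 sends major changes to primary endpoint definitions to an amendment, so the sponsor should record whether this is one. The statistical price is fewer rwRFS events and a wider interval, and a smaller sample if the analysis is limited to patients in remission.
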